Nasopharyngeal swab		X				X		
Prior/Concomitant medications	X	X	X	X	X	X	X	X
Adverse Events ^f		X	X	X	X	X	X	X

^a All vital signs (BP, pulse rate, and body temperature) will be measured at Screening in the supine position. On Day 1, temperature, blood pressure and pulse rate will be assessed.

^b See Section 10.5 for listing of tests

^c Opiates, benzodiazepines, amphetamines, cocaine, barbiturates, phencyclidine

^d At Screening and Day 1 WOCBP must have negative urine pregnancy test results

^e Review inclusion/exclusion criteria and may also include a limited physical examination

^f Any subject that experiences an AE (whether serious or non-serious) or has clinically significant abnormal laboratory tests will be followed until resolution or clinical stability up to 180 days after administration of the vaccine or longer if specified by the Investigator.

^g ET= early termination for any subject that discontinues prior to Day 29 visit, ET occurs after Day 29, the procedures for Day 181 will be followed.

^h Height and weight are not required at Day 1

SUMMIT ANALYTICAL

5 Analysis Populations

The following analysis populations will be used:

- **Safety Population:** All ALT-103-201 and ALT-FLZ-401 subjects who provide informed consent, are randomized, and receive at least 1 vaccination. The Safety Population will be used for all safety analyses and will be analyzed according to the treatment received.
- **Intent-to-treat (ITT) Population:** All ALT-103-201 and ALT-FLZ-401 subjects in the Safety Population who have HAI assay results on Day 1 and any postvaccination time point. The ITT Population is the secondary population for immunogenicity analyses. Analyses based on the ITT Population will be undertaken and presented only if >5% of subjects in any 1 dose group are excluded from the per-protocol population. The ITT population will be analyzed according to treatment as randomized.
- **Per-protocol (PP) Population:** All ALT-103-201 subjects in the Safety Population that received the assigned dose of the test article in accordance with the protocol; have HAI assay results on Days 1 and 29; and had no major protocol deviations affecting the primary immunogenicity outcomes as determined by the Sponsor prior to database lock. ALT-FLZ-401 subjects are included if they received the assigned dose of the test article in accordance with the protocol and have HAI assay results on Days 1 and 29. The PP Population is the primary population for immunogenicity analyses and will be presented regardless of whether subjects are excluded. The PP population will be analyzed as randomized.

SUMMIT ANALYTICAL

6 Analysis Variables

In what follows, variables to be analyzed have been grouped under the headings 6.1 to 6.4. Additional variables may be added as further drafts of the eCRF and this SAP are developed and/or as discussion unfolds concerning the usefulness of *derived* variables formulated using the information presented below.

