6.2 Randomization

Not applicable.

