NCI	New-onset Chronic Illness
PBMC	Peripheral Blood Mononuclear Cells

Abbreviation/Term	Definition
PP	Per-protocol
PT	Preferred Term
qPCR	Quantitative Polymerase Chain Reaction
SAE	Serious Adverse Event
SAP	Statistical Analysis Plan
SCR	Seroconversion Rate
SD or sd	Standard Deviation
SDTM	Study Data Tabulation Model
SFU	Spot-forming Unit
SOC	System Organ Class
SPR	Seroprotection Rate
SRC	Safety Review Committee
TEAE	Treatment Emergent Adverse Event
TFL	Tables, Figures, and Listings
vp	Viral Particles
WHO	World Health Organization

SUMMIT ANALYTICAL

2 Introduction

This document presents a statistical analysis plan (SAP) for Altimune, Inc. Protocol ALT-103-201, Single-ascending-dose Study of the Safety and Immunogenicity of NasoVAX.

Reference materials for this statistical plan include the Protocol ALT-103-201 Version 4.0 (dated 05 October 2017) and Electronic Case Report Forms (eCRF) (dated 02 September 2017).

Additionally, this plan incorporates a previous Phase 4 study of licensed seasonal vaccine in a similar subject population, ALT-FLZ-401, Extent and Durability of Immune Response Following Seasonal Influenza Vaccination in Healthy Volunteers. The reference materials for the comparison study include the Protocol ALT-FLZ-401 Version 1.0 (dated 26 April 2017) and eCRF (dated 02 May 2017). Disposition, demographic, and immunogenicity data from ALT-FLZ-401 will be included in the summaries described below.

The statistical plan described hereafter is an *a priori* plan. It will be submitted to file prior to any unblinded inferential or descriptive analyses of data pertaining to the Altimune, Inc. study ALT-103-201. This statistical plan disallows any analyses to be performed for any purpose prior to the unblinding of final study data and the submission to file of the final version of this plan. SAS programming may occur as study data accumulate in order to have analysis programs ready at the time the study finishes. In such an event, arbitrary dose group assignments must be randomly linked to subjects, effectively rendering any output of programs meaningless. For the reasons stated here the conduct of the study in the field is considered to be independent of any study outcome that might materialize upon enactment of the currently proposed statistical plan.

SUMMIT ANALYTICAL

3 Study Objectives and Endpoints

OBJECTIVES	ENDPOINTS
Primary Objective	

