7.2 Randomization

ALT-103-201 Subjects will be enrolled into 3 sequential cohorts of 20 subjects each defined by the viral particle dose (1×10^9 , 1×10^{10} , or 1×10^{11} vp). Within each sentinel group and cohort, subjects will be randomized at a ratio of 3:1 ratio to receive 1 intranasal dose of NasoVAX or placebo on Day 1.

A sentinel cohort of 5 subjects from each cohort will be dosed. Dosing of the remainder of each cohort may proceed after the last sentinel subject completes Day 8 if no events meeting stopping criteria (Section 6.6 of the ALT-103-201 protocol) have occurred. The SRC, consisting of the Investigator, the Medical Monitor, and a Sponsor Representative, will review all AE, reactogenicity, and laboratory data through Day 8 for all subjects in each cohort before subjects are randomized to the next higher dose.

No randomization was required for the ALT-FLZ-401 study.

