7.4 Analysis of the Study

All statistical tests will be two-sided and a difference resulting in a p-value of less than or equal to 0.05 will be considered statistically significant. All p-values will be rounded to and displayed in four decimals. If a p-value less than 0.0001 occurs it will be shown in tables as <0.0001.

There will be no multiplicity adjustments.

To integrate the 2 studies for the immunogenicity tables, figures, and listings (TFL), subjects enrolled in ALT-FLZ-401 will be treated as an additional arm in the ALT-103-201 study. ALT-FLZ-401 subjects will be denoted as "Fluzone" subjects in the TFL, while ALT-103-201 will be denoted as "NasoVAX" if they are assigned to an active dose, or placebo if appropriate.

Descriptive summaries of variables will be provided where appropriate. Continuous variables will be presented for each dose group by geometric means and 95% confidence intervals (CIs) for the immunogenicity endpoints and by summary statistics (e.g., mean, and standard deviation [SD], median, minimum, and maximum) for other endpoints. Categorical variables will be presented by frequency distributions (including percentages and 95% CIs) for the immunogenicity endpoints and frequency counts and percentages for other endpoints. Expansion of descriptive table categories within each dose group may occur if such elaborations are thought to be useful.

All collected data will be presented in listings. Data not subject to analysis according to this plan will not appear in any tables or graphs but will be included in the data listings.

Post-hoc exploratory analyses not identified in this SAP may be performed to further examine the study data. These analyses will be clearly identified as such in the final clinical study report.

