7.4.2 Study Data

For all summaries and analysis, ALT-103-201 subjects who are randomized to and/or treated with placebo from each of the 3 cohorts will be pooled into a single group.

Study data from the ALT-103-201 study will be integrated with data from the ALT-FLZ-401 in the analysis datasets; ALT-FLZ-401 will be treated as a separate dose group from the 4 arms of the ALT-103-201 study.

Study data identified in the schedule for time and events (Table 4-2) are collected, and source verified, on the electronic data capture (EDC) product Viedoc Clinic (Version 4.36) for the ALT-103-201 study, and on the ClinPlus Data Management System (3.3 SR2) for the ALT-FLZ-401 study. For the ALT-103-201 study, safety laboratory tests and viral culture are provided by ACM; the specialty laboratory vendors for tests that are not collected in the EDC tool are Altimmune UK (PBMC ELISpot), MPI (qPCR lab data [nasopharyngeal swab]), Battelle (Ad5 lab data [serum]), and Southern Research Institute (HAI and influenza MN [serum], and IgA lab data [nasopharyngeal swab]). For the ALT-FLZ-401 study, the Southern Research Institute will also be used for HAI, influenza MN, and IgA lab data; the analysis of these humoral response lab data will be completed simultaneously for both studies. The ALT-FLZ-401 study will also use Altimmune UK for the analysis of PBMCs, which will be completed simultaneously for both studies. Analysis of IgA lab data may be completed by a different specialty laboratory which will be determined prior to the end of the study. Samples which are being analyzed for both studies are pooled so that the lab will not know from which the study the sample was taken.

All study data will be formulated into regulatory compliant data sets to provide transparency, traceability, and integrity of trial analysis results from the collection source. Observed study data will be mapped to the CDISC Study Data Tabulation Model (SDTM) and serve as the source data from the trial. All study analyses will be completed using analysis data sets that are derived from the SDTM and follow the CDISC Analysis Data Model (ADaM) architecture. All planned analyses will be performed using the ADaM data sets developed for this study.

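### SAP 5 requires randomization for the Safety Population in both studies, so read literally none of the 20 unrandomized ALT-FLZ-401 subjects enters Safety or ITT

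*SAP*

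**What the plan says.** SAP 5 (Analysis Populations) gives one Safety definition for both studies: "All ALT-103-201 and ALT-FLZ-401 subjects who provide informed consent, are randomized, and receive at least 1 vaccination". The three conditions are joined, with no exception for either study. ITT is built on that set: "All ALT-103-201 and ALT-FLZ-401 subjects in the Safety Population who have HAI assay results on Day 1 and any postvaccination time point". It adds: "The ITT population will be analyzed according to treatment as randomized".

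On randomization in the Fluzone study, SAP 7.2 states: "No randomization was required for the ALT-FLZ-401 study". Protocol 6.2 has only the entry "Not applicable", and Protocol 3.1.2 describes a single treatment group.

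The SAP plainly expects Fluzone data in the outputs. SAP 2 says: "Disposition, demographic, and immunogenicity data from ALT-FLZ-401 will be included in the summaries described below". SAP 8.1 tabulates how many subjects of each study are in the Safety, ITT and PP sets. SAP 8.2 summarizes demographics for both studies on all three sets. SAP 8.4 summarizes concomitant medications for both studies, and SAP 10.1 assigns those tables to the Safety Population.

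**The concern.** A population definition is an instruction for setting a flag on each subject. Here a subject needs consent, randomization and a vaccination, and no ALT-FLZ-401 subject was randomized. The flag is therefore negative for the whole Fluzone group on Safety and, through the subset rule, on ITT. The same SAP asks for Fluzone results on those two sets, so the definition and the planned tables cannot both be followed.

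Most of what is at stake is descriptive: Fluzone columns for population counts, demographics and concomitant medications. One consequence is inferential but conditional. If ITT immunogenicity is triggered, its NasoVAX-versus-Fluzone comparisons would have nobody on the Fluzone side.

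**Working it through.** The plan has no calculated figure to reproduce on this point. The 20 ALT-FLZ-401 subjects were set on practical grounds (SAP 7.1). The check is a count of the conditions, followed by simple proportions.

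**Inputs**
- ALT-FLZ-401 subjects enrolled: 20 (SAP 4 and 7.1).
- ALT-FLZ-401 subjects randomized: 0 (SAP 7.2, Protocol 6.2).
- ALT-103-201 planned groups: 15 in each of three NasoVAX doses (SAP Table 4-1). Placebo is pooled over cohorts (SAP 7.4.2), giving 3 × 5 = 15.
- ITT immunogenicity trigger: more than 5% of any one dose group excluded from PP (SAP 5 and 8.6).

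**Fluzone membership as written**
- Safety = consent AND randomized AND vaccinated. The middle condition is met by 0 of 20, so Safety = 0 of 20.
- ITT = Safety AND Day 1 HAI AND any later HAI. It is a subset of an empty set, so ITT = 0 of 20.
- PP has a separate sentence for ALT-FLZ-401: assigned dose given per protocol, with HAI results on Days 1 and 29. It requires neither randomization nor Safety membership, so PP can hold up to 20 of 20.

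**Listed outputs that depend on these flags for Fluzone (SAP 10.1 with 8.1, 8.2 and 8.4)**
- Table 14.1.1, disposition: two of its three population counts (Safety and ITT) would be 0.
- Table 14.1.2.1, demographics on Safety.
- Table 14.1.2.2, demographics on ITT. This table is not conditional, so an ITT flag is needed even if ITT immunogenicity is never run.
- Tables 14.2.1 and 14.2.2, concomitant medications on Safety.

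That makes five tables.

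**Trigger for ITT immunogenicity**
- One exclusion in a 15-subject group: 1/15 = 6.7%, above 5%, so it fires.
- One exclusion among 20 Fluzone subjects: 1/20 = 5.0%, not above 5%, so it does not fire.
- Two exclusions among 20: 2/20 = 10%, so it fires.

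At planned sizes, a single exclusion in any of the four ALT-103-201 groups is enough. SAP Table 8-1 marks 6 of its 7 variables for comparison with ALT-FLZ-401. On a literal ITT set all six comparisons would have 0 Fluzone subjects.

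**After correction**
- If all 20 enrolled subjects consented and were vaccinated, Fluzone Safety goes from 0 to 20.
- Fluzone ITT goes from 0 to at most 20, depending on HAI results.
- The pooled Safety maximum goes from 60 to 60 + 20 = 80.
- Fluzone PP stays at a maximum of 20.

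**The case against.** The best defence is that nobody would program it this way. A sentence that opens by naming ALT-FLZ-401 cannot sensibly be meant to exclude everyone in it, and the ITT sentence names the study again. SAP 7.2 also shows why the condition cannot apply. The table shells and programming notes are a separate document that is not available here and may already set the flags correctly. All of this stands as to intent and likely practice. It does not make the text right: the PP definition gives ALT-FLZ-401 its own wording, while the Safety and ITT definitions do not.

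Three stronger readings are tempting but not supported.

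- A reader might infer a conflict with SAP 7.4, where "subjects enrolled in ALT-FLZ-401 will be treated as an additional arm in the ALT-103-201 study", and with SAP 7.4.2, where "ALT-FLZ-401 will be treated as a separate dose group from the 4 arms of the ALT-103-201 study". The first concerns the immunogenicity outputs and the second the analysis datasets. Every immunogenicity table and figure in SAP 10.1 is labelled per-protocol, and Fluzone subjects can enter PP, so both statements can hold as written.
- A reader might infer that ITT is the plan's check on a one-sided PP filter, because the major-deviation exclusion applies to ALT-103-201 only. SAP 5 calls ITT only the secondary immunogenicity set and gives it no such purpose. ITT also drops the Day 29 HAI requirement, so a difference between ITT and PP would not isolate deviations. Dosing outside the protocol is excluded from PP in both studies.
- A reader might see SAP 8.3 (no Fluzone deviations collected) as contradicting Protocol 6.6 (deviations to be documented and notified). Both can be true if deviations were documented but not entered in the database, and the matter is separate from this one.

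Analysing Fluzone as randomized is also empty wording, but harmless: with one treatment group, assignment as randomized and as treated cannot differ.

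**Conclusion.** The point holds as a minor error in a stated rule. Applied literally, SAP 5 puts 0 of 20 Fluzone subjects in Safety and ITT. That contradicts the Fluzone summaries planned in SAP 8.1, 8.2 and 8.4 across five tables, and it would leave any triggered ITT immunogenicity comparison with Fluzone without a comparator.

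It does not threaten the main results. Fluzone membership of PP, the primary immunogenicity set, is untouched. Safety analyses are restricted to ALT-103-201 (SAP 8.5). NasoVAX versus placebo involves the same subjects on every set, and SAP 3 lists the Fluzone comparison as exploratory.

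The membership count rests only on the documents' wording. The trigger arithmetic assumes the planned group sizes, and the corrected Safety count of 20 assumes that every enrolled Fluzone subject consented and was vaccinated.

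**What to change.** Split the Safety definition in SAP 5 by study, for example: *for ALT-103-201, subjects with informed consent who were randomized and received a vaccination; for ALT-FLZ-401, subjects with informed consent who were enrolled and received the vaccine.* ITT refers to Safety, so the correction carries over without a further edit. A note that ALT-FLZ-401 subjects are analysed as treated in ITT and PP would be tidy, but it is optional and changes no result.

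The cost is one reworded definition and a check that the population flags and shells agree with it. No analysis, table or data collection is added, because SAP 8.6 already calls for ITT immunogenicity when the threshold is passed.

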6.6 Protocol Deviations

The Investigator should conduct the study in compliance with the protocol agreed to by the Sponsor and, if required, by the regulatory authority(ies), and which that was given approval/favorable opinion by the IRB.

A deviation to any protocol procedure, or waiver to any stated criteria will not be allowed in this study except where necessary to eliminate immediate hazard(s) to the subject. The Sponsor must be notified of all intended or unintended deviations to the protocol (e.g., inclusion/exclusion criteria, dosing, missed study visits) on an expedited basis.

The Investigator, or person designated by the Investigator, should document and explain any deviation from the approved protocol.

If a subject was ineligible or received the incorrect dose or investigational treatment, and had one administration of IP, data should be collected for safety purposes.

The Investigator should notify the IRB of deviations from the protocol in accordance with local procedures.

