8.3 Protocol Deviations

Major protocol deviations for ALT-103-201 subjects, as determined by a sponsor-blinded review of the data prior to database lock and unblinding of the study, may result in the removal of a subject's data from the Per-protocol Population.

All protocol deviations will be presented in a data listing, with a flag to indicate if a violation resulted in the exclusion of the subject from the Per-protocol Population.

Protocol deviations were not collected for subjects in the ALT-FLZ-401 study.

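### The per-protocol set that leads the exploratory NasoVAX-versus-Fluzone contrasts removes major deviators from ALT-103-201 only, and Safety and ITT as worded require a randomisation that ALT-FLZ-401 never had

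*SAP*

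**What the plan says.** SAP section 5 defines three sets, each covering both studies.

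- **Safety:** "All ALT-103-201 and ALT-FLZ-401 subjects who provide informed consent, are randomized, and receive at least 1 vaccination".
- **ITT:** members of the Safety Population with HAI results on Day 1 and at any later visit. "The ITT population will be analyzed according to treatment as randomized". It is shown only if more than 5% of a dose group is excluded from PP.
- **PP, ALT-103-201:** Safety Population members dosed as assigned, with Day 1 and Day 29 HAI, who also "had no major protocol deviations affecting the primary immunogenicity outcomes as determined by the Sponsor prior to database lock".
- **PP, ALT-FLZ-401:** the HAI results needed are again those of Day 1 and Day 29. The rule reads: "ALT-FLZ-401 subjects are included if they received the assigned dose of the test article in accordance with the protocol and have HAI assay results". There is no deviation condition.
- **Status of PP:** "The PP Population is the primary population for immunogenicity analyses and will be presented regardless of whether subjects are excluded". On how its subjects are grouped, the SAP adds: "The PP population will be analyzed as randomized".

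SAP 7.2 and Protocol 6.2 both show that ALT-FLZ-401 had no randomisation. SAP 8.3 confines the review of major deviations to ALT-103-201 and adds: "Protocol deviations were not collected for subjects in the ALT-FLZ-401 study". Protocol 6.6 asks the investigator to document deviations and states: "The Sponsor must be notified of all intended or unintended deviations to the protocol".

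SAP section 3 lists the comparison with ALT-FLZ-401 as exploratory. SAP 8.6 compares each NasoVAX dose with Fluzone by ANCOVA at each visit, and by score intervals and Fisher's exact test for response rates. SAP 7.4 sets two-sided 0.05 with no multiplicity adjustment.

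**The concern.** There are two separate defects.

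The first is in the wording. A condition of being randomised cannot be met in a study that did not randomise, and analysing subjects as randomised has no meaning for them. If the rule is programmed as written, Fluzone drops out of every Safety and ITT table.

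The second is in the selection. The sponsor took care to make the two studies comparable: same site, entry criteria and immunogenicity schedule (SAP section 4), and samples pooled so that the laboratory could not tell which study they came from (SAP 7.4.2). The primary PP set then filters one side of the comparison for major deviations and leaves the other unfiltered. Blinding the review in SAP 8.3 hides NasoVAX from placebo, but it cannot hide study membership, because only ALT-103-201 subjects are reviewed.

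The two defects meet. ITT, as intended, is the one planned set with the same inclusion rule in both studies. As worded, it is also a set from which the comparator is absent. At stake is the reading of the NasoVAX-versus-Fluzone results, which are the only planned tests that compare ALT-FLZ-401 with another group.

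**Working it through.** The plan gives no figure for the effect of these rules. The only stated quantities are the 5% ITT trigger and the planned sizes: 15 per NasoVAX dose and 5 placebo in each of 3 cohorts, so 15 pooled placebo (SAP section 4 and 7.4.2), and 20 in ALT-FLZ-401 (SAP 7.1).

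**1. Who qualifies under the literal wording**

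- Safety requires consent, randomisation and vaccination. ALT-FLZ-401 subjects randomised: 0. So 0 of 20 qualify for Safety.
- ITT is a subset of Safety, so 0 of 20 qualify for ITT.
- The ALT-FLZ-401 sentence for PP does not refer to Safety, so the wording does not empty the Fluzone PP group.

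**2. PP conditions side by side**

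| Condition | ALT-103-201 | ALT-FLZ-401 |
|---|---|---|
| Assigned dose, per protocol | yes | yes |
| HAI on Days 1 and 29 | yes | yes |
| No major deviation affecting immunogenicity | yes | not applied |

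**3. When ITT is triggered** (excluded / group size > 5%)

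- NasoVAX dose or pooled placebo: 1/15 = 6.7%, triggers. One exclusion also triggers in a group as large as 19: 1/19 = 5.3%.
- Fluzone: 1/20 = 5.0%, does not trigger; 2/20 = 10% does.

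So at planned sizes, whenever the deviation filter removes anyone, ITT must also be presented.

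**4. Reach.** For A/California HAI titer alone, 3 doses × 6 post-baseline visits (Days 4, 8, 15, 29, 91, 181) = 18 ANCOVA contrasts with Fluzone are led by PP. This shows how far the rule extends. It does not measure bias.

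**5. How far the filter can move a NasoVAX response rate.** Remove m of 15 subjects, k of them responders, starting from r responders:

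shift = (r − k)/(15 − m) − r/15

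- m = 1, any r: at most ±6.7 points. Example: 14/14 − 14/15 = 100% − 93.3% = +6.7.
- m = 2, any r: at most ±13.3 points. Example: 13/13 − 13/15 = 100% − 86.7% = +13.3.
- With r between 5 and 10 (assumption), the limits are ±4.8 (10/14 − 10/15 = 71.4% − 66.7%) and ±10.3 (10/13 − 10/15 = 76.9% − 66.7%).

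The filter does not move the Fluzone rate. For scale, the exact 95% interval for an assumed 8/15 runs from 26.6% to 78.7%.

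These are arithmetic limits, not expected values. The documents do not give the number of major deviations, and SAP 8.3 says only that they may lead to removal.

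**The case against.** The strongest reply is that the plan largely handles this already. If the filter removes nobody, there is no asymmetry. If it removes one subject from a planned group of 15, ITT is presented as well. The separate rules are stated openly, SAP 8.3 gives a reason for them, and they share two of three conditions. The comparison is exploratory, non-randomised and not powered, and the possible shifts are small beside sampling error. All of this stands, and it is why the point is minor. It does not settle two things: PP still leads if the sets disagree, and ITT as worded has no Fluzone subjects.

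Three stronger readings are tempting, and the documents do not support them.

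- *The Fluzone arm is lost.* SAP 7.4, 7.4.2, 8.1 and 8.2 treat ALT-FLZ-401 as an added group and tabulate it in all the populations. The intent is clear; the rule is wrongly worded.
- *SAP 8.3 contradicts Protocol 6.6.* Deviations can be documented at the site and notified to the sponsor without being captured in the study data. The ALT-FLZ-401 case report form is not among the documents, so this needs clarifying but is not a shown contradiction.
- *The comparison is tilted towards NasoVAX.* That would require knowing how many deviators there were and how they responded. Neither is given, and deviators could shift the result in either direction.

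A further objection is that a symmetric deviation review would be hard to do. That is fair. ALT-FLZ-401 was open-label with one arm, so a blinded review has little meaning there. The Day 29 windows also differ: ±3 days in ALT-103-201 and ±1 day in ALT-FLZ-401 (SAP Tables 4-2 and 4-3). For that reason the fix relies on a common rule without a deviation filter.

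**Conclusion.** Both defects are established by the text, and the point is minor. Safety and ITT as worded admit 0 of 20 Fluzone subjects, against the evident intent. PP, the primary set, selects NasoVAX and Fluzone subjects under different rules.

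The effect on a NasoVAX response rate is bounded at 6.7 points for one exclusion and 13.3 for two, assuming the planned 15 per dose. The actual direction and size are unknown and may be zero.

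The NasoVAX-versus-placebo contrasts are not affected, because both groups pass through the same filter. The safety analyses are not affected, because SAP 8.5 limits them to ALT-103-201. The deviation filter leaves the Fluzone group's own estimates unchanged. No sample size, power or alpha figure changes.

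**What to change.** 1. **Wording.** In the Safety definition, write *randomized (ALT-103-201) or enrolled (ALT-FLZ-401)*. For ITT and PP, replace *as randomized* with *as assigned*.

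2. **Lead set for the Fluzone contrasts only.** Apply the existing ALT-FLZ-401 PP rule to both studies: assigned dose per protocol, HAI on Days 1 and 29, no deviation filter. Run this as a separate ANCOVA and separate rate comparisons, and let it lead if the sets disagree. Report the deviation-filtered PP contrasts as supportive, and state the one-sided filter as a limitation. Keep PP as primary for NasoVAX versus placebo.

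3. **Clarification.** State in SAP 8.3 whether ALT-FLZ-401 deviations were never recorded or only not captured in the study data, given what Protocol 6.6 asks for.

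**Cost.** Steps 1 and 2 need SAP wording and an additional model run on data already held; step 3 needs a check of site and sponsor files. A few NasoVAX deviators may stay in the Fluzone contrasts, and two sets of NasoVAX estimates will be reported, so tables should state which set each uses.
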